18.1.2 Deaths and Serious Adverse Events

A listing of deaths and other serious adverse events will be provided.

18.1.3 Laboratory Data

All laboratory data will be listed. A separate listing, including results with CTCAE (version 5.0) grade 3 or higher will also be provided. For listings, normal ranges will be used directly from the clinical laboratory.

For summaries, clinical laboratory data will be presented using Système International (SI) units (also used in the SDTM Controlled Terminology). Data will be standardized for units while site specific reference ranges for normal results will be maintained (in the standardized unit).

Hematology (including coagulation) and serum chemistry values at baseline, post-baseline and changes from baseline for each scheduled timepoint will be summarized.

For parameters with CTCAE grading, for all post-baseline results (scheduled and unscheduled) the shift to worst CTCAE grade after baseline grade will be identified per parameter and patient. This worst post baseline grade will be used in shift tables to summarize shifts from baseline using patient counts and percentages by treatment.

Pregnancy tests will be listed.

18.1.4 Vital Signs

Descriptive statistics will be provided to summarize vital signs and changes from baseline at each scheduled time and presented separately for each treatment group. All Vital Signs, including repeats in response to abnormalities, will be listed.

18.1.5 Electrocardiograms

Descriptive statistics will be provided to summarize ECG parameters and changes from baseline at scheduled time and presented separately for each treatment group, and overall.

ECG parameters will be listed.

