Aspartate aminotransferase (AST) and/or alanine aminotransferase (ALT)	
Grade 3 (> 5 and ≤ 20 × ULN)	Hold pamiparib until AST and/or ALT resolved to ≤ 5 × ULN or baseline 
 If not resolved within 7 days to ≤ 5 × ULN*, then pamiparib should be decreased by 1 dose level If second episode, permanently discontinue pamiparib *if other etiologies have been reasonably excluded and not solely based on abnormality/increase of AST/ALT laboratory results
Grade 4 (> 20 × ULN)	Permanently discontinue pamiparib
Pancreatic	
Pancreatitis	
Grade 3 or 4	Permanently discontinue pamiparib
Cardiac	
Cardiac - Prolonged QTc interval	
QTcF > 500 msec or Change in QTc interval > 60 msec from the highest value at baseline or predose	
 Obtain triplicate electrocardiograms (2 to 3 minutes apart) ~1 hour after initial electrocardiogram If mean QTcF > 500 ms or mean change in QTc interval > 60 msec, hold pamiparib until evaluation of electrocardiograms by cardiologist 
 Cardiology evaluation as soon as practical but within 7 days of initial abnormal electrocardiogram If mean QTcF > 500 ms or mean change in QTc interval > 60 msec is confirmed by cardiologist, permanently discontinue pamiparib
Cardiac – General	
Grade 3	Hold pamiparib until resolved to Grade ≤ 1 or baseline and ↓ pamiparib by 1 dose level 
 In the event of acute coronary syndrome, congestive heart failure and myocardial infarction, treatment should be permanently discontinued
Grade 4	Permanently discontinue pamiparib

Toxicity	Recommended Dose Modification ^a
Other AEs	
Grade 3	Hold pamiparib until resolved to Grade \leq 1 or baseline and ↓ pamiparib by 1 dose level No dose reduction required for asymptomatic laboratory abnormalities
Grade 4	Permanently discontinue pamiparib

Abbreviations: AE = adverse event; ALT = alanine aminotransferase; ANC = absolute neutrophil count; AST = aspartate aminotransferase; BID = twice daily; Hgb = hemoglobin; MDRD = Modification of Diet in Renal Disease; PLT = platelet (count); QTc = QT interval corrected for heart rate; QTcF = QT interval corrected for heart rate using Fridericia's formula; ULN = upper limit of normal.

- a. Dosing of pamiparib can be withheld for up to 28 days consecutively (up to 56 days consecutively for investigational drug-related anemia).

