8.2.3 Vital Signs

Supine blood pressure, supine pulse rate, respiratory rate, and body temperature will be assessed at the times indicated in the Schedule of Assessments in [Appendix 1](#). Vital signs may also be performed at other times if judged to be clinically appropriate or if the ongoing review of the data suggests a more detailed assessment of vital signs is required.

All measurements will be performed singly and repeated once if outside the relevant clinical reference range.

Patients must be supine for at least 5 minutes before blood pressure, heart rate, and temperature measurements. During the in-house period of the Core Phase, blood pressure, heart rate, and temperature measurements should be conducted in the morning. When scheduled at the same time, vital sign assessments are to be performed prior to PK blood draws, with blood draws to occur as close to the nominal times as possible except for Screening and Day -1.

8.2.4 12-Lead Electrocardiogram

Resting 12-lead ECGs will be recorded after the patient has been supine and at rest for at least 5 minutes at the times indicated in the Schedule of Assessments in [Appendix 1](#).

Single 12-lead ECGs will be repeated once if either of the following criteria apply postdose:

- QTcF > 500 msec
- QTcF change from the baseline (predose) is > 60 msec

Additional 12-lead ECGs may be performed at other times if judged to be clinically appropriate or if the ongoing review of the data suggests a more detailed assessment of ECGs is required. The investigator (or designee) will perform a clinical assessment of each 12-lead ECG. When numerous assessments are scheduled at the same time, ECGs are to be performed prior to vital sign assessments and PK blood draws, with PK blood draws to occur as close to the nominal times as possible except for Screening and Day -1.

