9.1.3 Descriptive Statistics

Unless otherwise indicated, continuous variables will be summarized with the following descriptive statistics: n (number of observations), (arithmetic) mean, standard deviation (SD), minimum (min) value, median, and maximum (max) value.

Where calculated, Geometric CV (%) = $\sqrt{\exp(S^2) - 1} \times 100$, where S^2 is the sample variance of PK parameters in the logarithmic scale.

Categorical data will be summarized with frequencies and percentages. Percentages by categories will be based on the number of patients exposed within a category of interest.

For categorical data the categories will be presented in the tables exactly as they appear in the CRF / Database. No data manipulation will be done for presentation purposes.

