9.1.5 Unscheduled Measurements

Unscheduled measurements will be included in the listings. With the exception of unscheduled measurements used to define baseline or to define the largest change of CTCAE grade in shift table, unscheduled measurements will be excluded from the descriptive statistics and statistical analysis.

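### The SAP plans no count of patients crossing the protocol's QTc limits, and unscheduled ECGs are listed but left out of the ECG summaries

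*SAP*

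**What the plan says.** **Protocol.** Section 8.2.4 has a postdose ECG repeated when either of two limits is met: "QTcF > 500 msec" or "QTcF change from the baseline (predose) is > 60 msec". The prolonged-QTc row of Table 2 (Section 6.7) uses the same two numbers for pamiparib. It asks for triplicate ECGs about an hour later and a cardiology evaluation, and its last step reads "confirmed by cardiologist, permanently discontinue pamiparib". ECG parameters are a secondary endpoint (Protocol 3.2, SAP 5.2.2).

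**SAP.** Section 18.1.5 has two elements. The first is the summary: "Descriptive statistics will be provided to summarize ECG parameters and changes from baseline at scheduled time". The second is that "ECG parameters will be listed". Section 9.1.3 defines the summary statistics as "n (number of observations), (arithmetic) mean, standard deviation (SD), minimum (min) value, median, and maximum (max) value". Section 9.1.5 states "Unscheduled measurements will be included in the listings", and then that "unscheduled measurements will be excluded from the descriptive statistics and statistical analysis", with exceptions only for defining baseline and for the largest CTCAE grade change in a shift table. The only shift table described is for laboratory data (18.1.3). It counts patients by worst post-baseline grade and uses scheduled and unscheduled results. The SAP body mentions neither QTcF nor the 500 and 60 msec limits.

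**The concern.** The protocol treats QTc prolongation as something that happens to a patient at a threshold. The planned ECG output describes a distribution at each scheduled time. These answer different questions, and the question the protocol acts on (how many patients crossed a limit) is not answered by any ECG table the SAP describes.

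The rule on unscheduled measurements makes this worse, because the ECGs most likely to carry the information are the ones left out: the repeats under Protocol 8.2.4, the Table 2 triplicates, and any ECG prompted by symptoms. For laboratory data the SAP foresaw the same problem and made an exception. For ECGs it did not. At stake is whether the study report gives a direct, per-patient account of a safety signal on which the protocol can stop treatment.

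**Working it through.** The documents give no figure to reproduce here: the sample size is not power-based and nothing is calculated for ECGs. The check is a comparison of texts, followed by simple illustrations.

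**Step 1. Which ECGs enter the summary?** This reads protocol-required repeats as unscheduled, in line with SAP 9.2.1, which groups unscheduled and repeated measurements together.

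| ECG | Source | In ECG summary? | In listing? |
|---|---|---|---|
| Core Phase, predose and 2 h postdose on Days 1 and 10 (Part A) or Days 1 and 7 (Part B) | Schedule of Assessments | Yes | Yes |
| Core Phase, Day 12 (A) or Day 9 (B), and EOT | Schedule of Assessments | Yes | Yes |
| Repeat after a limit is crossed | Protocol 8.2.4 | No | Yes |
| Extension Phase, Predose and EOT | Schedule of Assessments | Yes | Yes |
| Extension Phase, any ECG during dosing | Not scheduled | No | Yes |
| Table 2 triplicates | Protocol 6.7 | No | Yes |

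The EOT ECG need not be done if one was taken in the preceding 14 days (Protocol 8.3 and Schedule footnote g). A patient could therefore exceed a limit on a prompted ECG, have the triplicates, stop pamiparib and have the EOT ECG waived. That patient would contribute no on-treatment Extension ECG to any ECG summary.

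**Step 2. What does the summary show when a scheduled ECG crosses the limit?** Inputs: 12 patients per part (SAP 6.1). Assumption, for illustration only: patients below the limit have a change of 0.

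- One patient at +65 msec: mean = 65/12 = 5.4, SD 18.8, median 0, maximum 65. Patients over 60 msec: 1/12 = 8.3%.
- Three patients at +65, +62 and +61 msec: mean = (65 + 62 + 61)/12 = 188/12 = 15.7, SD 28.4, median 0, maximum 65. Patients over 60 msec: 3/12 = 25.0%.

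The median and maximum are identical. The mean and SD differ, but they do not give the count. Nor can tables by time point be added across times: a maximum above 60 msec on two days may be one patient or two.

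**Step 3. How informative would the count be?** The chance of seeing at least one patient over a limit among 12 is 1 − (1 − p)^12. For assumed true rates p of 2%, 5% and 10% this is 21.5%, 46.0% and 71.8%. If none crosses, the one-sided 95% upper bound is 1 − 0.05^(1/n): 25.9% for n = 10, 22.1% for n = 12 and 11.7% for n = 24. The table would report what happened; it would not exclude a modest risk.

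**Step 4. Which baseline defines the change?**

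- SAP 9.2.1: the last observation before first study drug, plus a second Core Phase ECG baseline before coadministration. No separate Extension Phase baseline is given.
- Protocol 8.2.4: the predose baseline, with QTcF for both limits.
- Protocol Table 2: the highest value at baseline or predose, with QTcF for the absolute limit but QTc, correction unspecified, for the change.

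A count of changes above 60 msec can differ according to which of these is used, so the table must name its reference.

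**The case against.** The strongest reply is that little would actually be hidden, and much of it stands.

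- A reader might infer that ECGs are reported only as averages. They are not: minimum and maximum are planned, so a scheduled change of +65 msec prints as the maximum.
- A reader might infer that unscheduled ECGs disappear. They do not: they stay in the listings, and with about 12 patients per part each one can be found there. A scheduled ECG that triggers a repeat also stays in the summary; only the repeat leaves it.
- A reader might infer that a patient who stopped pamiparib for QTc prolongation would go unreported. That is unlikely. Protocol 9.1.5 gives dose interruption or discontinuation among the usual marks of a clinically significant abnormality, which is recorded as an adverse event. It would then reach the SAP 18.1.1 tables and the listing of events leading to discontinuation. SAP 11.0 also summarizes reasons for treatment discontinuation.
- The SAP does not depart from the protocol. Protocol 11.4 promises only that ECG values will be listed and summarized descriptively.
- Table 2 falls under the Extension Phase rules, so the 12-per-part illustration does not describe it directly.
- The list of outputs named in the SAP contents (Appendix 3) is not in the available text, so it cannot be said that no such table exists anywhere.

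What the reply does not remove: the adverse event route depends on the investigator's judgment and gives no count against either limit, and a listing leaves the counting to the reader.

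**Conclusion.** The point holds as a gap in secondary safety reporting. The SAP body plans no number or percentage of patients over the protocol's QTc limits, and its rule on unscheduled measurements keeps repeat and prompted ECGs out of the ECG summaries. In the Core Phase the loss is moderate, because a scheduled exceedance still shows as a maximum. In the Extension Phase it is larger, because no ECG during dosing is scheduled; an exceedance seen only then is in the listing but in no ECG summary.

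This rests on the SAP body without the output list, and on reading repeats as unscheduled. The documents do not support saying that exceedances would be concealed or that the SAP breaches the protocol. The primary pharmacokinetic analysis and the sample size are not touched. It should be corrected, and correcting it is easy.

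**What to change.** 1. Add a table to SAP 18.1.5: number and percentage of patients with worst post-baseline QTcF above 500 msec, and with maximum QTcF increase above 60 msec, by part and treatment and for the Extension Phase. Use all post-baseline ECGs (scheduled, repeat and unscheduled), and state the number of ECGs per patient.
2. Add the worst ECG value to the exceptions in SAP 9.1.5, alongside the CTCAE grade shift.
3. State the baseline for each period, consistent with the two baselines in SAP 9.2.1, and say which applies in the Extension Phase.
4. Reconcile the baseline and QTc/QTcF wording of Protocol 8.2.4 and Table 2, so that the count refers to a single stated definition. How that is settled is for the sponsor; this point proposes no clinical rule.

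The cost is one extra table from data already collected. Its drawback is that worst-value counts rise with the number of ECGs taken, so patients with more prompted ECGs have more chances to cross a limit. Showing the number of ECGs per patient makes that visible.

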18.1.6 Other Observations Related to Safety

ECOG Performance Status will be listed and summarized descriptively .

Physical examination data will be listed by patient

Appendix 1: Glossary of Abbreviations

Glossary of Abbreviations:	
ADaM	Analysis Data Model
AE	Adverse Event
AUC	Area under the curve
BMI	Body Mass Index
BQL	Below the Quantifiable Limit
CL	Clearance
CRF	Case Report Form
CSR	Clinical Study Report
CTCAE	Common Terminology Criteria for Adverse Events
CV	Coefficient of variation
ECG	Electrocardiogram
ECOG	Eastern Cooperative Oncology Group
EDS	Early Development Services
ICH	The International Conference on Harmonization of Technical Requirements for Registration of Pharmaceuticals for Human Use
LLOQ	Lower Limit of quantification
LS	Least Square
PK	Pharmacokinetic
QA	Quality Assured
QC	Quality Controlled
SAP	Statistical Analysis Plan
SD	Standard Deviation
SDTM	Standard Data Tabulation Model
SEM	Standard Error of Mean
TEAE	Treatment-emergent Adverse Event
TFL	Tables, Figures and Listings
WNL	WinNonlin

Appendix 2: Schedule of Assessments

Schedule of Assessments: Part A

Study Procedures	Screening	Core Phase					Safety Follow-up Visit (≤30 days after last dose) ^p
	Days -28 to -1 ⁿ	Day -1	Day 1	Days 2 to 11	Day 12	Core Phase EOT Visit (≤7 days after last dose)	
Informed consent	X						
Inclusion/exclusion criteria	X						
Confirm eligibility (laboratory values) ^a		X					
Demographic data ^b	X						
Medical history ^c	X						
ECOG Performance Status	X						
Urine drug screen	X	X					
Alcohol breath test	X	X					
Serum pregnancy test/FSH ^d	X (Days -7 to -1)						
Height, BMI ^e	X						
Weight	X	X			X		
Serology (HBV, HCV) ^f	X						
Study drug administration^g							
Pamiparib Dosing			X	Day 10			
Rifampicin Dosing				Days 3 to 11			
Pharmacokinetics							
Blood samples for pamiparib concentration			X (30 min predose, 0.5, 1, 2, 4, 6, 9, 12, 24, and 48 hours postdose)	Day 10: 30 min predose, 0.5, 1, 2, 4, 6, 9, 12, 24, and 48 hours postdose			
Safety and tolerability							
Adverse event recording	X	X	X	X	X	X	X

Prior/concomitant medication recording	X	X	X	X	X	X	X
--	---	---	---	---	---	---	---

Schedule of Assessments: Part A (Continued)

Study Procedures	Screening	Core Phase					Safety Follow-Up Visit (≤30 days after last dose) ^p	
		Days -28 to -1 ⁿ	Day -1	Day 1	Days 2 to 11	Day 12		Core Phase EOT Visit (≤7 days after last dose)
Clinical chemistry, hematology and urinalysis ^h	X	X				X	X	X
Vital signs ⁱ	X	X	X (30 min predose and 1, 2, 4, and 24 hours postdose)	Day 10: 30 min predose and 1, 2, 4, and 24 hours postdose	X	X	X	X
12-lead ECG ^j	X		X (30 min predose and 2 hours postdose)	Day 10: 30 min predose and 2 hours postdose	X	X		
Complete physical examination ^k	X	X						
Limited physical examination ^l			X	X (Day 10)	X	X		X
CT or MRI ^m	X							

Abbreviations: BMI = body mass index; CT = computed tomography; ECG = electrocardiogram; EOT: end of treatment; FSH = follicle-stimulating hormone; MRI = magnetic resonance imaging; PK = pharmacokinetic; SAE = serious adverse event.

- a. Confirmation of eligibility: all laboratory values obtained on Day -1 must meet eligibility criteria.
- b. Demographic data: Date of birth, gender, ethnicity, and race must be recorded.
- c. Medical History/Current Medical Conditions: General and disease specific medical history including a history of past and current medical conditions.
- d. For females of childbearing potential, a highly sensitive serum pregnancy test must be performed at a central or local laboratory within 7 days before Day 1. For subsequent pregnancy testing, highly sensitive urine pregnancy tests, performed at a central or local laboratory, are allowed. If a urine pregnancy test is positive, a confirmatory serum pregnancy test is required.
- e. Height will be measured at Screening only for BMI calculation.
- f. Serology: hepatitis B surface antigen, hepatitis B surface antibody, hepatitis B Core antibody, and hepatitis C antibody
- g. On Day 1 and Day 10, patients are required to fast for at least 8 hours before and 4 hours after pamiparib and rifampin administration. Water is allowed during the fasting period. On Day 10, rifampin will be administered first, followed within 5 minutes by pamiparib. On Days 3-9 and Day patients are required to fast for 2 hours before and 1 hour after rifampin administration.
- h. Blood samples for clinical laboratory evaluations (clinical chemistry, hematology, and urinalysis) will be collected after at least an 8-hour fast. If Screening urinalysis and chemistry and hematology laboratory evaluations were performed within 3 days of Day-1, they do not need to be repeated on Day-1.
- i. Vital signs include supine blood pressure, supine pulse rate, respiratory rate, and body temperature. Patients are to remain supine for at least 5 minutes prior to blood pressure and pulse rate measurements. When scheduled at the same time, vital sign assessments are to be performed prior to PK blood draws, with blood draws to occur as close to the nominal times as possible except for Screening and Day -1.

-
- j. Patients are to remain supine for at least 5 minutes prior to ECG assessments. When numerous assessments are scheduled at the same time, ECGs are to be performed prior to vital sign assessments and PK blood draws, with PK blood draws to occur as close to the nominal times as possible except for Screening and Day -1.
 - k. Complete physical examination at Screening and Day -1.
 - l. Limited physical examination to occur on Days 1, 10 and 12, EOT and Safety Follow-up includes assessment of general appearance and additional examination of symptomatic systems or those affected by the patient's disease.
 - m. A computed tomography (CT) or MRI scan of the thorax, abdomen, and pelvis plus other relevant evaluations as appropriate will be performed at Screening.
 - n. All assessments obtained within 3 days of Day -1 do not have to be repeated on Day -1.
 - o. Check-out takes place on Day 12 after all procedures have been completed.
 - p. All patients, including those who withdraw early from the study, will have an EOT visit within 7 days after the last dose of rifampicin. Safety Follow-up in the Core Phase is only to be conducted if the patient does not continue to the Extension Phase. All patients who permanently discontinue study drug will have a Safety follow-up approximately 30 days after the last day of study drug or before initiation of new anticancer therapy, whichever occurs first. AEs and SAEs will be collected; clinical laboratory assessment should only be conducted if the patient had an ongoing clinical laboratory abnormality in the previous visit, which the PI considers to be related to study drug. If no laboratory assessments are required, the patient should be contacted by telephone for a review of AEs/concomitant medications and the limited physical exam will not be performed.

Schedule of Assessments: Part B

Study Procedures	Screening		Core Phase				Safety Follow-Up Visit (≤30 days after last dose) ^P
	Days -28 to -1 ⁿ	Day -1	Day 1	Days 2 to 8	Day 9	Core Phase EOT Visit (≤7 days after last dose)	
Informed consent	X						
Inclusion/exclusion criteria	X						
Confirm eligibility (laboratory values) ^a		X					
Demographic data ^b	X						
Medical history ^c	X						
ECOG Performance Status	X						
Urine drug screen	X	X					
Alcohol breath test	X	X					
Serum pregnancy test/ FSH ^d	X (Days -7 to -1)						
Height, BMI ^e	X						
Weight	X	X			X		
Serology (HBV, HCV) ^f	X						
Study drug administration ^g							
Pamiparib Dosing			X	Day 7			
Itraconazole Dosing				Days 3 to 8			
Pharmacokinetics							
Blood samples for pamiparib concentration			X (30 min predose, 0.5, 1, 2, 4, 6, 9, 12, 24, and 48 hours postdose)	Day 7:30 min predose, 0.5, 1, 2, 4, 6, 9, 12, 24, and 48 hours postdose			
Safety and tolerability							
Adverse event recording	X	X	X	X	X	X	X
Prior/concomitant medication recording	X	X	X	X	X	X	X

Schedule of Assessments: Part B (Continued)

Study Phase	Screening	Core Phase					Safety Follow-Up Visit (≤30 days after last dose) ^p	
		Day of Phase	Days -28 to -1 ⁿ	Day -1	Day 1	Days 2 to 8		Day 9
Clinical chemistry, hematology and urinalysis ^h	X	X				X	X	X
Vital signs ⁱ	X	X	X (30 min predose and 1, 2, 4, and 24 hours postdose)	Day 7: 30 min predose and 1, 2, 4, and 24 hours postdose		X	X	X
12-lead ECG ^j	X		X (30 min predose and 2 hours postdose)	Day 7: 30 min predose and 2 hours postdose		X	X	
Complete physical examination ^k	X	X						
Limited physical examination ^l			X	X (Day 7)		X	X	X
CT or MRI ^m	X							

Abbreviations: BMI = body mass index; CT = computed tomography ECG = electrocardiogram; EOT: end of treatment; FSH = follicle-stimulating hormone; MRI = magnetic resonance imaging; PK = pharmacokinetic; SAE = serious adverse event.

- Confirmation of eligibility: all laboratory values obtained on Day -1 must meet eligibility criteria.
- Demographic data: Date of birth, gender, ethnicity, and race must be recorded.
- Medical History/Current Medical Conditions: General and disease specific medical history including a history of past and current medical conditions.
- For females of childbearing potential, a highly sensitive serum pregnancy test must be performed at a central or local laboratory within 7 days before Day 1. For subsequent pregnancy testing, highly sensitive urine pregnancy tests, performed at a central or local laboratory, are allowed. If a urine pregnancy test is positive, a confirmatory serum pregnancy test is required.
- Height will be measured at Screening only for BMI calculation.
- Serology: hepatitis B surface antigen, hepatitis B surface antibody, hepatitis B Core antibody, and hepatitis C antibody
- On Day 1 and Day 7, patients are required to fast for at least 8 hours before and 4 hours after pamiparib and itraconazole administration. Water is allowed during the fasting period. Itraconazole will be administered approximately 30 minutes after completing a meal on Days 3 to 6 and 8. On Day 7, itraconazole will be administered first, followed within 5 minutes by pamiparib.
- Blood samples for clinical laboratory evaluations (clinical chemistry, hematology, and urinalysis) will be collected after at least an 8-hour fast. If Screening urinalysis and chemistry and hematology laboratory evaluations were performed within 3 days of Day-1, they do not need to be repeated on Day-1.

-
- i. Vital signs include supine blood pressure, supine pulse rate, respiratory rate, and body temperature. Patients are to remain supine for at least 5 minutes prior to blood pressure and pulse rate measurements. When scheduled at the same time, vital sign assessments are to be performed prior to PK blood draws, with blood draws to occur as close to the nominal times as possible except for Screening and Day -1.
 - j. Patients are to remain supine for at least 5 minutes prior to ECG assessments. When numerous assessments are scheduled at the same time, ECGs are to be performed prior to vital sign assessments and PK blood draws, with PK blood draws to occur as close to the nominal times as possible except for Screening and Day -1.
 - k. Complete physical examination at Screening and Day -1.
 - l. Limited physical examination to occur on Days 1, 7 and 9, EOT and Safety Follow-up includes assessment of general appearance and additional examination of symptomatic systems or those affected by the patient's disease.
 - m. A computed tomography (CT) or MRI scan of the thorax, abdomen, and pelvis plus other relevant evaluations as appropriate will be performed at screening
 - n. All assessments obtained within 3 days of Day -1 do not have to be repeated on Day- 1.
 - o. Check-out takes place on Day 9 after all procedures have been completed.
 - p. All patients, including those who withdraw early from the study, will have an EOT visit within 7 days after the last dose of itraconazole. Safety Follow-up visit in the Core Phase is only to be conducted if the patient does not continue to the Extension Phase. All patients who permanently discontinue study drug will have a Safety follow-up approximately 30 days after the last day of study drug or before initiation of new anticancer therapy, whichever occurs first. AEs and SAEs will be collected; clinical laboratory assessment should only be conducted if the patient had an ongoing clinical laboratory abnormality in the previous visit, which the PI considers to be related to study drug. If no laboratory assessments are required, the patient should be contacted by telephone for a review of AEs/concomitant medications and the limited physical exam will not be performed.

Schedule of Assessments Extension Phase

Study Procedures	Predose Visit (≤ 7 days prior to Cycle 1 Day 1) ^e	Cycles 1 and 2		Cycle ≥ 3 ^f	EOT visit ^g	Safety Follow-up Visit (≤30 days after last dose) ^h
		Day 1 ⁱ	Day 15	Day 1		
Allowed time window (days)		± 2	± 2	± 2		
Body Weight	X	X		X	X	
ECOG performance status		X		X	X	
Urinalysis	X				X	
Vital Signs ^a	X				X	
12-Lead ECG ^b	X				X	
Limited Physical examination ^c	X	X		X	X	X
Clinical chemistry and hematology	X	X	X	X	X	X ^j
Pregnancy test	X	X		X	X	
Pamiparib administration ^d		X (60 mg PO twice daily)				
Tumor assessments (CT or MRI scan)		X (every 8 weeks ± 7 days)				
Adverse event recording	X	X	X	X	X	X
Concomitant medication	X	X	X	X	X	X

Abbreviations: CT = computed tomography ECG = electrocardiogram; ECOG = Eastern Cooperative Oncology Group; EOT: end of treatment; MRI = magnetic resonance imaging; PO = orally.

- Vital Signs: Blood pressure, heart rate, and temperature must be measured after the patient has been supine for 5 minutes at Screening and EOT.
- Single 12-lead ECGs will be repeated once if outside the clinical reference range, or there is other clinically significant finding. Repeat ECGs will be recorded in triplicate at least 2 minutes apart. ECGs will be recorded after the patient has been supine for 5 minutes.
- Limited physical examination: includes assessment of general appearance and additional examination of symptomatic systems or those affected by the patient's disease. For the follow-up visit, the limited physical examination is only to be done if this visit is conducted while the patient is attending the clinic.
- Dosing: Pamiparib capsules should be administered continuously from Cycle 1 Day 1 (60 mg twice daily), until patients are discontinued from treatment.
- Predose visit: Assessments performed in the Core Phase Follow-up visit for Part 1 may be used as the predose visit for the Extension Phase if it occurs ≤ 7 days prior to the start of pamiparib treatment in Extension Phase.
- Cycle 3+: Cycles will continue as long as the patient is experiencing clinical benefit, or until occurrence of progressive disease (PD), unacceptable toxicity, pregnancy, death, withdrawal of consent, lost to follow-up, major protocol violation which in the opinion of the sponsor would have significant impact on the study or its outcome, start of new anticancer therapy, withdrawal by the PI, or study termination by sponsor.

-
- g. End-of-Treatment (EOT) Visit: To occur within 7 days after the last day of study drug administration. A visit should be scheduled as soon as possible, but may occur later after discussion with the medical monitor for specific circumstances, such as prolonged hospitalization. An ECG does not need to occur at the EOT Visit if one was performed within 14 days prior to the visit.
 - h. Safety Follow-up Visit: To occur approximately 30 days after the last day of study drug administration or before initiation of new anticancer therapy, whichever occurs first. If new anticancer therapy is initiated before this safety follow-up, a safety follow-up should be scheduled as soon as possible. Clinical laboratory evaluations are only required if the patient had an ongoing clinical laboratory abnormality at the previous visit that the principal investigator considered to be related to study drug. For patients who do not want to or cannot return to the clinic for the safety follow-up, the patient should be contacted by telephone for a review of adverse events.
 - i. Cycle 1 Day 1: Assessments will be conducted prior to first dosing in the Extension Phase.
 - j. Follow-up assessments: only to be conducted if the patient has an ongoing laboratory abnormality at the previous visit that the PI considers to be related to the study drug.

Document History

Version Date	Modified/Reviewed By	Brief Summary of Changes (if created from a template, include template code)
06 Nov 2019	[REDACTED]	Created from template EDSREP 009 T 01 E
21 Nov 2019	[REDACTED]	Modified based on sponsor comments
11 Dec 2019	[REDACTED]	Modified based on sponsor comments
18 Dec 2019	[REDACTED]	Final draft version
19 Dec 2019	[REDACTED]	Final version 1

Signature Page for VV-CLIN-083944 v1.0

Approval	 Biometrics 16-Mar-2022 16:58:07 GMT+0000
----------	---

Signature Page for VV-CLIN-083944 v1.0
